8.4.2.4 Sponsor's Reporting Responsibilities

Events reported to the sponsor will be promptly evaluated and will be reported as required according to FDA IND safety reporting guidance and regulations. IND safety reports will be sent to other investigators conducting research under the same IND and will be shared with other stakeholders according to applicable agreements.

The sponsor will also submit an IND annual report of the progress of the investigation to the FDA as defined in 21 CFR 312.33.

All UPs will be evaluated by the sponsor, and a summary of the event, and any necessary (corrective/preventative) actions, will be distributed to investigators conducting research under the same IND as may be relevant and appropriate.

8.4.3 Withdrawal Criteria for an Individual Subject

An individual subject will be withdrawn from the study for any of the following:

• An individual subject's/parent's/guardian's decision. (The investigator should attempt to determine the reason for the decision.)

Version Date: 14 March 2024

• Non-compliance with study procedures to the extent that it is potentially harmful to the subject or to the integrity of the study data.

- A change in the subject's condition as follows:
 - o Loss of the ability of the subject/parent/guardian to provide informed consent.
 - o Withdraws permission to have blood samples or data stored for future research.
 - o Positive pregnancy test prior to study agent administration.
- The investigator determines that continued participation in the study would not be in the best interest of the subject.

8.4.3.1 Re-enrollment and Unplanned Procedure Repetition

Unless otherwise specified within this protocol (e.g., rescreening as described in section 5.6), each person who is a subject in this study may be enrolled and may pass through each step and process outlined in the protocol, only **ONCE** (i.e., subjects may not "go back" and repeat a protocol step already completed). On a case-by-case basis, a request for re-enrollment, or for repetition of a protocol step or procedure already completed, may be submitted to, reviewed by, and approved by the SMM in writing. The SMM may also recommend or require consultation of the EC and/or DSMB and ISM.

8.4.3.2 Replacement of Withdrawn Subjects or Subjects Who Discontinue Study Agent

In the dose-escalation study, subjects withdrawn prior to the day 7 safety evaluation will be replaced. In the efficacy study, subjects withdrawn prior to study agent administration will be replaced. Subjects who are withdrawn in the year 2 extension study will not be replaced.

All subjects exposed to study agents MUST be included in the safety dataset.

8.4.4 Additional Safety Oversight

8.4.4.1 Safety Review and Communications Plan

A safety review and communication plan (SRCP) is required for this protocol. The SRCP is an internal communications document between the principal investigators and the CSO, as sponsor representative, which delineates key safety oversight responsibilities of the principal investigators, the CSO, and other stakeholders. The SRCP includes a plan for conducting periodic safety surveillance assessments by the CSO.

8.4.4.2 Sponsor Medical Monitor

A SMM, representing the sponsor, has been appointed for oversight of safety in this clinical study. The SMM will be responsible for performing safety assessments as outlined in the SRCP.

Version Date: 14 March 2024

8.4.4.3 Oversight Committees

8.4.4.3.1 Independent Safety Monitor in Mali

The ISM is an expert who does not have direct involvement in the conduct of the study and has no significant conflicts of interest as defined by NIAID policy. An ISM in Mali will review the study prior to initiation and will be available to advise the investigators on study-related medical issues and act as a representative for the welfare of the subjects. The ISM will conduct independent safety monitoring. The ISM is an expert in the field of oversight of clinical trials conducted in Mali and internal medicine, specifically in the population under study in Mali.

All deaths, SAEs, UPs, pregnancies, and FDA IND safety reports will be reported by the principal investigators to the ISM prior to or at the same time they are submitted to the EC or CSO unless otherwise specified herein. The ISM will be notified immediately if any pausing rule is met. The principal investigators will also notify the ISM if intentional or unintentional unblinding occurs. If the ISM is unblinded to the study agent given to an individual subject during medical management, the ISM will report that unblinding to the DSMB Executive Secretary. The ISM will have access to unblinded data, by group, only as the entire DSMB does. The ISM may also serve as an *ad hoc* member of the DSMB.

8.4.4.3.2 Data and Safety Monitoring Board

The NIAID intramural DSMB includes independent experts that do not have direct involvement in the conduct of the study and have no significant conflicts of interest as defined by NIAID policy. The DSMB will review the study protocol, consent documents, and investigator brochure prior to initiation and twice a year thereafter, or as may be determined by the DSMB. Additionally, the DSMB will conduct 1 interim analysis when safety data are available from the dose-escalation study subjects (section 9.5.8). They will also review available data from Year 1 of the study prior to starting participant visits for Year 2.

The DSMB may convene additional reviews as necessary. The DSMB will review the study data as needed to evaluate the safety, efficacy, study progress, and conduct of the study.

All deaths, SAEs, UPs, pregnancies, and IND safety reports will be reported to the DSMB at the same time they are submitted to the EC and CSO unless otherwise specified herein.

All cases of intentional or unintentional unblinding will be reported to the DSMB not later than 1 business day from the time of study personnel awareness.

The principal investigators will notify the DSMB at the time pausing or halting criteria are met and obtain a recommendation concerning continuation, modification, or termination of the study.

Version Date: 14 March 2024

8.4.5 Pausing Rules

"Pausing" is discontinuation of study intervention/treatment/dosing (agent/placebo/procedure, etc.) in a protocol-defined group or "arm," until a decision is made to either resume or permanently discontinue such activity. Subjects continue to be followed for safety during a pause.

The pausing criteria for a group or arm (e.g., a specific dosing group) in this study include any one or more of the following:

- A subject experiences an SAE that is unexpected (per the investigator's brochure or product label) and possibly, probably, or definitely related to a study agent;
- A subject experiences 2 grade 3 or greater AEs that are unexpected (per the investigator's brochure or product label) and possibly, probably, or definitely related to a study agent.

The principal investigators or the CSO may also pause dosing/study interventions for one or more subjects for any safety issue. The study safety oversight bodies (e.g., DSMB, ISM) may recommend a pause to the CSO.

8.4.5.1 Reporting a Pause

If a pausing criterion is met, a description of the AE(s) or safety issue must be reported by the principal investigators within 1 business day to the CSO and the EC according to their requirements. The principal investigators will also notify the DSMB and ISM. In addition, the CSO or designee will notify all other site investigators by email or through the specified pathway.

8.4.5.2 Resumption Following a Pause

The CSO, in collaboration with the principal investigators and DSMB and ISM, will determine if study activities, including agent administration and/or other study interventions may be resumed, and any additional modifications or requirements that may apply, for the impacted subject(s), or whether the events that triggered the pause require expansion to a study halt (see below).

The CSO or sponsor designee will notify the principal investigators of the decision. The principal investigators will notify the EC of the decision according to the EC's process.

8.4.5.3 Discontinuation of Study Agent

If a decision is made to permanently discontinue study agent administration, any subject who has received the study agent or undergone any other study intervention/treatment will continue to be followed for protocol-specified safety assessments or as clinically indicated, whichever is more conservative.

Version Date: 14 March 2024

8.4.6 Halting Rules for the Protocol

"Halting" is discontinuation of study intervention/treatment/dosing (agent/placebo/procedure, etc.) for all subjects in a study and suspension of enrollment until a decision is made to either resume or permanently discontinue such activity. Subjects continue to be followed for safety during a halt.

The halting rules are:

• Two or more subjects experience the same or similar grade 3 or greater AEs that are unexpected and possibly, probably, or definitely related to a study agent;

OR

 Any safety issue that the principal investigators or the CSO determines should halt the study. The study safety oversight bodies (e.g., DSMB) may recommend a halt to the CSO.

In addition, the FDA, Malian Ministry of Health, FMOS/FAPH EC, or any regulatory body having oversight authority may halt the study at any time. The DSMB or ISM may recommend a study halt.

8.4.6.1 Reporting a Study Halt

If a halting criterion is met, a description of the AE(s) or safety issue must be reported by the principal investigators, within 1 business day to the CSO and the EC according to their requirements. The principal investigators will also notify the DSMB and ISM. In addition, the CSO or designee will notify all other site investigators by email or through the specified pathway.

8.4.6.2 Resumption of a Halted Study

The CSO, in collaboration with the principal investigators and DSMB and ISM will determine if study activities, including enrollment, study agent administration, and/or other study interventions, may be resumed and any additional modifications or requirements that may apply.

The CSO or sponsor designee will notify the principal investigators of the decision. The principal investigators will notify the EC of the decision according to the EC's process.

8.4.6.3 Discontinuation of Study Agent

If a decision is made to permanently discontinue study agent administration, any subjects who have received study agent or undergone any other study intervention will continue to be followed for protocol-specified safety assessments or as clinically indicated, whichever is more conservative.

Version Date: 14 March 2024

8.5 Unanticipated Problems

8.5.1 Definition of Unanticipated Problems

The definition of a UP is provided in section 8.4.1.

8.5.2 Unanticipated Problem Reporting

The investigator will report UPs to the FMOS/FAPH EC according to NIH Human Research Protection Program (HRPP) Policy 801, as described in section 8.6.1.

8.6 ADDITIONAL REPORTING REQUIREMENTS

8.6.1 Reporting to the FMOS/FAPH EC

Non-compliance and other reportable events will be reported to the FMOS/FAPH EC according to NIH HRPP Policy 801, which requires reporting as described below.

The following will be reported within 7 calendar days of any investigator or individual associated with the protocol first becoming aware:

- Actual or suspected noncompliance. Determinations by the FMOS/FAPH EC of serious and/or continuing non-compliance by an NIH investigator must also be reported to the NIH within 7 calendar days.
- Actual or suspected major deviation.
- Actual or suspected UPs.
- New information that might affect the willingness of a subject to enroll or remain in the study.
- Suspension or termination of research activities, including holds on new enrollment, placed upon the research by the sponsor, NIH or NIAID leadership, or any regulatory agency.

Any death of a research subject that is possibly, probably, or definitely related to the research must be reported within 24 hours of the investigator becoming aware of the death.

Additionally, investigators must provide the following information to the EC in summary format at the time of continuing review, or when otherwise specifically requested by the EC or the NIH Office of Human Subjects Research Protections Office of Compliance and Training:

- Major and minor protocol deviations.
- Noncompliance reported to the EC that is not related to a protocol deviation.
- AEs and SAEs that do not meet the definition of an UP.
- UPs reported to the EC.

Version Date: 14 March 2024

8.6.2 Reporting to the NIAID Clinical Director

The principal investigator will report UPs, major protocol deviations, and deaths to the NIAID clinical director according to institutional timelines.

8.6.3 Reporting Protocol Deviations that Result from the COVID-19 Pandemic

The following addresses the reporting requirements to the FMOS/FAPH EC with regard to protocol deviations that result from disruption of study visits from the COVID-19 pandemic. These requirements follow the direction of the FMOS/FAPH EC as well as the NIH reporting requirements.

Investigators may modify the protocol without prospective FMOS/FAPH EC approval when necessary to prevent an immediate apparent harm to a study subject. Typically, when this occurs the event must be reported to the EC via a Reportable Event Form (REF) within 7 days of the deviation. Given the potential need for this to occur on a much larger than usual scale, it is not required that all planned deviations be reported to the FMOS/FAPH EC in an expedited timeframe. Only those deviations which meet the definition of a major deviation will require reporting, as defined in section 8.4.1.

If a subject cannot complete a protocol-specified study visit or intervention, the principal investigator should assess the impact of the missed visit on the safety of the subject and the scientific validity of the trial. If in the principal investigator's determination neither of these are meaningfully impacted by the deviation, these do not need to be reported to the FMOS/FAPH EC in an expedited manner. The event should be included in the summary of events reported at the time of continuing review.

If in the opinion of the principal investigator the missed visit or intervention poses a risk to the safety of the subject, the investigator should develop a plan to minimize the impact of the deviation. For example, if the subject is scheduled to return to the study site for safety lab work, the investigator may arrange for labs to be drawn at a location closer to the subject's home. In cases such as this, if the change is necessary to assure the safety of the subject, the investigator may implement the change without prospective FMOS/FAPH EC approval. If the change meets the definition of a major deviation, it must be reported via a REF within 7 days.

9 STATISTICAL CONSIDERATIONS

9.1 Statistical Hypothesis

The primary study hypotheses are that L9LS will be safe and will confer protection against Pf infection. In the dose-escalation study, the primary objective is to evaluate the safety and tolerability. In the efficacy study, the primary objective is to evaluate the efficacy of L9LS compared to placebo.

Version Date: 14 March 2024

Primary Endpoints:

• Dose escalation and efficacy: Incidence and severity of local and systemic AEs occurring within 7 days after the administration of L9LS.

• Efficacy: Pf blood-stage infection as detected by microscopic examination of thick blood smears obtained between 1 week and 24 weeks after administration of L9LS or placebo.

Secondary Endpoints:

Data from both parts of the study will be used to assess the following endpoints:

- Measurement of L9LS in sera of recipients.
- Pf blood-stage infection as detected by RT-PCR for 28 weeks after administration of L9LS or placebo for the dose escalation study and for 24 weeks after administration of L9LS or placebo for the efficacy study.
- Incidence of clinical malaria (definition 1, see section 2.2.2.3) for 28 weeks after administration of L9LS or placebo for the dose escalation study and for 24 weeks after administration of L9LS or placebo for the efficacy study.
- Incidence of clinical malaria (definition 2, see section 2.2.2.3) for 28 weeks after administration of L9LS or placebo for the dose escalation study and for 24 weeks after administration of L9LS or placebo for the efficacy study.
- PK analysis of L9LS and the association of L9LS concentration with Pf infection risk.
- PK analysis of L9LS and the association of L9LS concentration with clinical malaria risk.

9.2 Sample Size Determination

9.2.1 Sample Size Considerations for the Dose-Escalation Study

The ability of the study to identify safety events can be expressed in terms of the probability of observing 1 or more event of interest (e.g., AEs) within each arm. With sample size n=6 in each arm, there is over 90% chance to observe at least 1 AE if the true rate is at least 0.319 and over a 90% chance to observe no AE if the true rate is no more than 0.017. With sample size n=9 in each arm, there is over a 90% chance to observe at least 1 AE if the true rate is at least 0.226 and over a 90% chance to observe no AE if the true rate is no more than 0.011. Probabilities of observing 0 or more than 1 AE within a group are presented in Table 3 for a range of possible true event rates.

Table 3. Probability of events for different safety scenarios within an arm (n=6 or n=9).

True event	n=6		e event n=6 n=9		=9
rate	Pr(0)	Pr(>1)	Pr(0)	Pr(>1)	
0.005	0.97	< 0.001	0.956	0.001	
0.01	0.941	0.001	0.914	0.003	
0.02	0.886	0.006	0.834	0.013	

Version Date: 14 March 2024

True event	n=6		n=6		n	n=9
rate	Pr(0)	Pr(>1)	Pr(0)	Pr(>1)		
0.035	0.808	0.017	0.726	0.037		
0.05	0.735	0.033	0.63	0.071		
0.1	0.531	0.114	0.387	0.225		
0.15	0.377	0.224	0.232	0.401		
0.2	0.262	0.345	0.134	0.564		
0.3	0.118	0.58	0.04	0.804		

Abbreviations: Pr, probability.

9.2.2 Sample Size Considerations for the Efficacy Study

The efficacy study is designed to evaluate protective efficacy (PE) of L9LS at each dose by testing the null hypothesis,

H0: PE = 0%,

versus the alternative hypothesis,

H1: PE \neq 0%,

where PE is 1 minus the relative risk of infection under L9LS versus under placebo. To account for the two comparisons, each L9LS dose arm with the placebo arm, two-sided tests each with significance level of 0.025 will be adopted to ensure the overall type I error rate is no more than 0.05. The sample size considerations are based on the power of rejecting H0 over a range of possible protective efficacy and infection rates under placebo (Figure 5). Assuming a drop-out rate of 10%, Table 4 presents the power under a 2-sided log-rank test with significance level of 0.025. If the infection rate under placebo is 0.4, there will be 90% power to detect the protective efficacy of 0.7 with 75 participants enrolled into each arm of the efficacy study. Based on historical data collected in Kalifabougou, approximately 85% of children aged 6-10 years who are uninfected (PCR negative) before the malaria season become infected with Pf during the ensuing malaria season (Figure 5). Therefore, the conservative estimate of infection rate under placebo of 0.4 will ensure that the study has adequate power if the malaria season is unexpectedly delayed or truncated.

Table 4. Power for efficacy evaluation from a 2-sided log-rank test with type I error rate of 0.025 assuming 10% dropout.

	Infection rate		
Sample size	under	Protective	Power
(per arm)	placebo	efficacy	(%)
60	0.4	0.6	68
	0.4	0.7	83
	0.4	0.8	92
	0.5	0.6	82

Version Date: 14 March 2024

	0.5	0.7	92
	0.5	0.8	97
	0.6	0.6	92
	0.6	0.7	97
	0.6	0.8	99
75	0.4	0.6	78
	0.4	0.7	91
	0.4	0.8	97
	0.5	0.6	90
	0.5	0.7	97
	0.5	0.8	99
	0.6	0.6	97
	0.6	0.7	99
	0.6	0.8	100

Table 5 presents the minimum detectable difference between an L9LS arm and placebo arm in terms of the event rate, for example the proportion of infection, based on a two-sided proportion test with type I error rate of 0.025.

Table 5. Minimum detectable difference in the event rate in arms receiving L9LS or placebo under a 2-sided type I error rate of 0.025.

Sample	Event rate	Detectable with 80% power		Detectable with 90% power	
size within each arm (#)	(under placebo)	Difference	Event rate (under L9LS)	Difference	Event rate (under L9LS)
75 under	0.4	0.226	0.174	0.253	0.147
L9LS and	0.5	0.243	0.257	0.273	0.227
75 under placebo	0.6	0.25	0.35	0.283	0.317
piacebo	0.7	0.247	0.453	0.282	0.418

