9.3 Sample Size Considerations for the Year 2 Extension Study

For safety assessment, Table 6 shows the precision for estimating the AE rate within each arm of 42 participants for a range of underlying event rates.

Table 6. Exact 95% CI of AE rate estimate within each arm of size 42.

Observed		95% confidence interval	
number of	Observed	Lower	Upper
events	event rate	bound	bound
0	0	0	0.084

Version Date: 14 March 2024

1	0.024	0.001	0.126
2	0.048	0.006	0.162
3	0.071	0.015	0.195
4	0.095	0.027	0.226
5	0.119	0.04	0.256
6	0.143	0.054	0.285
7	0.167	0.07	0.314
8	0.19	0.086	0.341
9	0.214	0.103	0.368
10	0.238	0.121	0.395
11	0.262	0.139	0.42
12	0.286	0.157	0.446
13	0.31	0.176	0.471
14	0.333	0.196	0.495

With 42 participants per arm, there is 90% power to detect the difference between two arms if the event rate is 0.01, 0.05, or 0.1 in one arm and no less than 0.24, 0.33, or 0.42 in the other arm, respectively, based on two-sided proportion test at significance level 0.05.

Table 7 shows the power for comparing two arms on the primary efficacy endpoint, namely, the time from receiving the second dose of L9LS (or placebo) to the first Pf blood-stage infection during extension study with each arm of 42 participants.

Table 7. Power for between-arm comparison on time to infection based on two-sided log rank test at significance level 0.05.

Infection rate	Infection rate in		
in one arm	the other arm	Relative efficacy	Power (%)
0.5	0.2	0.6	79
0.5	0.15	0.7	90
0.6	0.24	0.6	89
0.6	0.18	0.7	96
0.7	0.28	0.6	96
0.7	0.21	0.7	99

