9.5.4 Efficacy Analyses

The primary efficacy endpoint (efficacy study primary endpoint) is the incidence of malaria infection defined as blood smear—positive Pf infection between 1 week and 24 weeks after administration. The secondary efficacy endpoints are the incidence of malaria infection as determined by RT-PCR and the incidence of clinical malaria. The efficacy analyses will be MITT over participants in the efficacy study.

Version Date: 14 March 2024

The primary efficacy analysis will be based on time to the first infection. The survival patterns will be described by Kaplan-Meier curves for each arm and compared by the logrank test across different arms. The protective efficacy of the study product will be estimated by the hazard ratio from the Cox proportional hazards model. These analyses will be carried out by R packages that account for interval censoring: package "interval" for deriving a nonparametric maximum likelihood estimation based on the Kaplan-Meier survival curve and logrank test, and package "icenReg" for Cox proportional hazards regression. To address the heterogeneity of the study population, a Cox regression with regressors other than the study arm will be additionally performed to account for potential differences among participants. The regressors will include time of enrollment and possibly those covariates that are significantly different between the study product arms and the placebo arm in spite of randomization. An additional Cox regression will be performed with pre-existing parasitemia (Pf infection status determined by blood smear at baseline) as the stratification variable. The Holm method will be adopted to handle the issue of multiplicity in comparing the two dose arms against the placebo.

The secondary efficacy analysis will be based on the proportion of infection. The proportion of infection will be estimated for each arm and compared across arms based on Kaplan-Meier estimates assuming events occur at the time they are detected: the proportion of infection by one minus the Kaplan-Meier estimate in the arm, and the vaccine efficacy by one minus the relative risk of infection with melding method for constructing the melded 95% CI of the vaccine efficacy.³⁷

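### Does Table 5 need restating because, unlike Table 4, it makes no allowance for dropout?

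*Combined protocol and SAP*

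**What the plan says.** Section 9.2.2 sets 75 children per arm and tests each L9LS dose against placebo at a two-sided 0.025. On the log-rank comparison it says: "Assuming a drop-out rate of 10%, Table 4 presents the power under a 2-sided log-rank test with significance level of 0.025". The Table 4 caption repeats the 10%.

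Table 5 follows with the same arms and the same alpha. Its caption is "Table 5. Minimum detectable difference in the event rate in arms receiving L9LS or placebo under a 2-sided type I error rate of 0.025", and its lead-in describes the difference "in terms of the event rate, for example the proportion of infection, based on a two-sided proportion test". The sample-size column gives 75 under L9LS and 75 under placebo. Dropout is not mentioned.

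Two other sections bear on how Table 5 should be read. Section 9.5.4 says of the secondary efficacy analysis: "The proportion of infection will be estimated for each arm and compared across arms based on Kaplan-Meier estimates". Section 8.4.3.2 says: "In the efficacy study, subjects withdrawn prior to study agent administration will be replaced".

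Section 9.3, for the Year 2 extension, works at 42 per arm throughout. For safety: "With 42 participants per arm, there is 90% power to detect the difference between two arms", at the rates listed there, "based on two-sided proportion test at significance level 0.05". Table 7 concerns the time "to the first Pf blood-stage infection during extension study with each arm of 42 participants". The Synopsis gives ceilings of 84 children for each of arms 1 and 2 and 93 for arm 3, and limits entry to those still enrolled who agree to continue. Table 1 lists sub-arms of 42, 42, 42, 42, 46 and 46.

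**The concern.** Two adjacent tables print the same 75 for the same arms at the same alpha, but the number means different things: in Table 4 it is enrolment, discounted by 10%; in Table 5 it is the analysed number. A reader coming from Table 4 could assume that the allowance carries over and take Table 5 as more reassuring than it is. At a placebo rate of 0.4, Table 4 gives 78% power for a difference of 0.24 (efficacy 0.6), while Table 5 gives 80% for a smaller difference, 0.226.

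Section 9.3 raises a similar doubt. Since 84/2 = 42, its figures hold for arms 1 and 2 only if nobody is lost or declines, and extension withdrawals are not replaced. The safety sentence also does not say which proportion test it uses. If these tables fixed the sample size, the trial could be smaller than its stated power requires.

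**Working it through.** **Table 4 reproduced.** Inputs from section 9.2.2: placebo rate p0, L9LS rate p1 = p0(1 − PE), two-sided alpha 0.025 (z = 2.241). Freedman's formula: HR = ln(1 − p1)/ln(1 − p0), events d = n(p0 + p1), power = Φ(√d × (1 − HR)/(1 + HR) − z).

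For p0 = 0.4 and PE = 0.6, p1 = 0.16 and HR = ln(0.84)/ln(0.60) = 0.341.
- n = 0.9 × 75 = 67.5: d = 67.5 × 0.56 = 37.8, power 78.2%. Printed: 78%.
- n = 75: d = 42.0, power 82.7%.

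All 18 cells match within 0.5 points at 0.9n; without the discount the gap reaches 4.7 points. The 10% is built in.

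**Table 5 reproduced.** Pooled two-proportion test: power = Φ{[Δ√n − z√(2p̄(1 − p̄))] / √(p0(1 − p0) + p1(1 − p1))}, where p̄ is the mean of p0 and p1.

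For p0 = 0.4, Δ = 0.226: p1 = 0.174, p̄ = 0.287, and the two square roots are 0.6397 and 0.6195.
- n = 75: (1.957 − 2.241 × 0.6397)/0.6195 = 0.845, power 80.1%.
- n = 67.5: (1.857 − 2.241 × 0.6397)/0.6195 = 0.683, power 75.3%.

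| Placebo rate | Printed difference, 80% / 90% | Solved at 75 | Solved at 67.5 | Power of printed differences at 67.5 |
|---|---|---|---|---|
| 0.4 | 0.226 / 0.253 | 0.226 / 0.253 | 0.236 / 0.264 | 75.3% / 86.5% |
| 0.5 | 0.243 / 0.273 | 0.242 / 0.273 | 0.254 / 0.286 | 75.5% / 86.5% |
| 0.6 | 0.250 / 0.283 | 0.249 / 0.282 | 0.262 / 0.297 | 75.5% / 86.5% |
| 0.7 | 0.247 / 0.282 | 0.247 / 0.281 | 0.260 / 0.297 | 75.3% / 86.5% |

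Every cell is right, within 0.001, at the 75 the table prints.

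**Why the two tables disagree.** Dropout is only part of it. For 0.4 against 0.16, the two-proportion formula gives 85.8% at 75 and 81.5% at 67.5; Freedman gives 82.7% and 78.2%. Restating Table 5 at 67.5 would still leave 81.5% against 78.2%.

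**Dropout as the plan would analyse it.** A child lost mid-season stays in a Kaplan-Meier estimate until lost. Simulation assumptions: exponential infection times, 10% of children censored uniformly over follow-up, 75 per arm, Wald test on Kaplan-Meier proportions with Greenwood variance, alpha 0.025. Over the four placebo rates:
- At the 80% differences: 80.6 to 82.0% with no loss, 79.0 to 79.2% with 10% censored.
- At the 90% differences: 90.5 to 91.6% with no loss, 88.6 to 89.9% with 10% censored.

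A repeat with 40,000 runs agreed (78.7 to 79.6% and 88.8 to 89.8%). The Wald test is slightly liberal here (size 2.8 to 2.9%) and stands in for the melded interval the plan will use, so the drop of roughly 1 to 3 points is more reliable than the absolute level.

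**Section 9.3.** Table 7 matches Freedman at n = 42 with alpha 0.05: 79.4, 90.0, 89.3, 95.8, 95.6 and 98.6% against the printed 79, 90, 89, 96, 96 and 99%. At the safety sentence's rates (0.01 vs 0.24, 0.05 vs 0.33, 0.10 vs 0.42), Fisher's exact test at 42 has 90.2, 90.9 and 91.0% power, so that is evidently the test used. The section states no loss rate, so the sizes below 42 are assumptions.

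| n per sub-arm | Fisher power, three pairs | Exact power of pooled z-test | Upper 95% limit, 0 events |
|---|---|---|---|
| 42 | 90.2 / 90.9 / 91.0% | 97.1 / 94.6 / 94.2% | 8.4% |
| 40 | 87.8 / 89.0 / 89.1% | 96.4 / 93.5 / 93.0% | 8.8% |
| 38 | 84.9 / 86.8 / 87.2% | 95.5 / 92.1 / 91.7% | 9.3% |
| 34 | 77.3 / 81.1 / 81.7% | 92.9 / 89.0 / 89.1% | 10.3% |

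At 38, the Freedman values for Table 7 fall by 1 to 4 points, but simulated log-rank power (80.7, 92.8, 91.0, 97.7, 97.2 and 99.7%) is above every printed row, because the formula is conservative here.

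**The case for a change.** The best case for a change is that printing 75 does not settle the matter, since Table 4 prints 75 too and discounts it. Infection is Table 5's own example of an event, replacement covers only withdrawal before dosing, and so later dropout does affect that comparison. Safety is a primary extension objective, so the test behind the 90% sentence could reasonably be named. The cost would be a few labels.

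That stands as a remark on presentation. It does not stand as a reason to restate the numbers. Table 4 says where its allowance applies; Table 5 claims none and shows its n. Deleting 10% outright is harsher than the planned analysis. Table 5 covers event rates in general, and section 9.5.5 also compares proportions with adverse events; for 7-day events a table at 67 per arm would understate what is available. In section 9.3 a row at 38 would rest on a loss rate the plan does not give. The ceilings are already in the Synopsis and the sub-arm sizes in Table 1; for arm 3 (93 split into 46 and 47) the figure of 42 is below the maximum. Extension numbers depend on who remains and agrees, not on these tables.

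**Conclusion.** The asymmetry is real, but no change to the plan follows. Every figure checked is correct at its printed sample size, and the missing words (before dropout, maximum, Fisher's exact test) are details that a statistician can supply from the tables, the Synopsis and Table 1.

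For infection, taking Table 5 without a dropout allowance costs about 5 points at nominal 80% and 3.5 at nominal 90% if dropouts are deleted. Under the planned Kaplan-Meier comparison with 10% evenly spread censoring, power is about 79% and 89 to 90%, so the stated power is essentially delivered. Even spread is an assumption; earlier dropout would move the result towards the deletion figures.

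The choice of 75 per arm rests on Table 4, which includes dropout and uses a placebo infection rate of 0.4, against about 0.85 historically by PCR. Neither enrolment, nor an analysis, nor a conclusion depends on how Table 5 or section 9.3 is labelled.
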